6.6.1. Exposure

6.6.1.1. Number of Injections and Exposure Days to rFVIII Fc

For any patient, the total number of days of exposure to rFVIII Fc will be accumulated from the time of their first on-study injection of rFVIII Fc. An ED is a 24-hour period in which one or more rFVIII Fc injections are given. The 24-hour window starts from the first injection on study and then for subsequent injections, it starts from an injection taken after/outside of a previously identified ED.

The total number of EDs on rFVIII Fc for each patient will be summarized categorically (<5, 5-<10, 10-<20, 20-<50, 50-<75, 75-<100 and >=100) and with descriptive statistics for the Safety Analysis Set.

The total number of injections per patient will be summarized overall and by reason for injection (prophylactic regimen, ITI regimen, spontaneous bleed, traumatic bleed, follow-up injection, surgical or other) using descriptive statistics for the Safety Analysis Set.

These tables will be presented by treatment regimen and for the inhibitor subgroups, as described in Sections 5.1.1.1 and 5.1.1.2 respectively.

The total number of injections and EDs will also be summarized by EPD entry compliance (see Section 6.6.2.3), <80% and >=80%, where >=80% is considered compliant.

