### 7.3. Overall Study Duration and Follow-Up

The study period will consist of screening, treatment, and follow-up. Individual subject study participation is expected to be approximately 6 months to 3 years, including screening and follow-up. For subjects who do not develop an inhibitor, the treatment period is no less than 50 EDs to the study treatment.

One ED is defined as a 24-hour period in which a subject receives 1 or more doses of rFVIII Fc, with the time of the first injection of rFVIII Fc defined as the start of the ED.

See [Figure 1](#) for a schematic of the study design.

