### 10.2.7. Immune Tolerance Induction Therapy

Subjects who develop high titer inhibitors as defined in Section 10.2.5.2.2 and choose to remain in the study will undergo ITI with rFVIII Fc, as described below. Subjects with low titer inhibitors as defined in Section 10.2.5.2.1 will be eligible for ITI if the Investigator determines that bleeding is no longer adequately controlled despite increased rFVIII Fc doses or if bypassing agents are required to treat bleeding in a subject with a positive low titer inhibitor (see Section 5.3). Separate consent is required before starting an ITI regimen.

The timing of ITI initiation in patients with a peak inhibitor titer of >10 BU/mL, including patients who experience serious or life-threatening bleeding or have frequent mild to moderate bleeding, will be based on the Investigator's clinical judgement.

If an investigator chooses to have the subject temporarily suspend treatment with rFVIII Fc, and delay the start of ITI, the subject should continue to participate in Interim visits every  $12 \pm 2$  weeks (per the prophylaxis schedule in Section 4.2.2.1).

The ITI regimen will approximate the high-dose treatment arm of the International ITI Study protocol [Hay and DiMichele 2012] and will utilize single injections of rFVIII Fc 200 IU/kg, daily. Concomitant immunomodulation will not be allowed during ITI therapy.

ITI outcomes will be assessed on an ongoing basis as described in Section 10.2.7.4. Additional informed consent must be obtained prior to the ITI assessments beginning at Day 0.

Immune tolerance induction therapy assessments will be performed according to the schedule as described in Section 4.2.2.3.

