3.1.2.3. Immune Tolerance Induction (ITI) Treatment Regimen

After exposure to rFVIII Fc, any patient who develops a positive high-titer inhibitor or a positive low-titer inhibitor (both defined in Section 5.1.2.4) with poorly controlled bleeding, is eligible to undergo an ITI regimen with rFVIII Fc. The ITI treatment regimen consists of single injections of rFVIII Fc 200 IU/kg/day, consistent with current ITI guidelines.² Duration of ITI treatment is up to 33 months, followed by a tapering off regimen of at least 3 months (12 weeks). Separate consent is required before starting an ITI treatment regimen.

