6.6.2.2. Compliance of Prophylactic Injections

The compliance rate of each patient to the prescribed prophylactic and ITI dosing regimens during the efficacy period will be calculated in 2 ways: As dose compliance and as dosing interval compliance. Compliance will first be determined on a per-injection basis and then on a per-patient basis. That is, compliance for an individual dose or dosing interval will be determined and then the overall percentage of doses and dosing intervals that were in compliance will be determined for each patient.

For the purpose of evaluating compliance, the following will be considered per injection:

- The nominal dose taken compared to the nominal dose prescribed
- The actual day of treatment compared to the prescribed day of treatment

An individual dose will be considered compliant if it is within 80%-125% of the prescribed dose. An individual dosing interval will be considered compliant if the time between two prophylactic doses is within 24 hours of the prescribed dosing interval. Prescribed dose and dosing intervals are according to the Investigator. Instructions provided to the patient by the Investigator regarding dose or dosing interval changes will be used to determine compliance as of the date the information was provided to the patient.

The actual dosing intervals will be calculated as the length of time between consecutive prophylactic doses (date/time of PR_{x+1} – date/time of PR_x), PR_{x+1} and PR_x. The actual time between doses will be determined in minutes and converted to days as the number of minutes divided by 1440. The prescribed dosing interval will be taken from the eCRF as recorded by the Investigator. The absolute value of the difference between the actual and prescribed dosing intervals must be ≤1 day (+/- 24 hours) in order to be compliant, or +/- 12 hours for ITI regimens, as these are daily dosing or more frequent.

All prophylactic injections will be used to determine prophylactic dose compliance; only the prophylactic injections used to determine the average prophylactic dosing interval (i.e., intervals not separated by a bleeding episode or surgical/rehabilitation period), as detailed in Section 5.4, will be used to evaluate prophylactic interval compliance. Dose and dosing interval compliance rates per patient will be determined as follows:

$$\text{Dose compliance rate} = \frac{\text{Number of doses taken within 80\%-125\% of prescribed dose}}{\text{Total number of doses}} \times 100$$

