9.4.3.2. Primary Analysis

The primary analysis of overall incidence of positive inhibitor formation, is based on all patients who have reached at least 10 EDs and had at least one inhibitor test performed at or beyond this milestone. Additionally, any patient who develops an inhibitor following the initial rFVIII Fc

	Statistical Analysis Plan	Final v1.0
---	----------------------------------	-------------------

administration will be included in the numerator and denominator. Patients who do not develop an inhibitor but reached the milestone number of EDs will be included in the denominator, i.e.,:

$$\text{Incidence rate} = \frac{\text{Number of patients with an inhibitor}}{\text{Number of patients reaching ED milestone or who have an inhibitor}}$$

An exact 95% confidence interval for the proportion of patients with a positive inhibitor will be calculated using the Clopper-Pearson method for a binomial proportion. PROC FREQ in SAS version 9.4 or higher will be used to produce this confidence interval.

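### The 24-hour exposure-day rule can drop daily doses given under 24 h after the current ED opened, so ED totals during ITI understate dosing days by an amount set by clock-time variation

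*SAP*

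**What the plan says.** Protocol 7.3 sets the unit: "One ED is defined as a 24-hour period in which a subject receives 1 or more doses of rFVIII Fc", with the window starting at the first injection. Protocol 16.5.2.1 and SAP 3.1 and 5.1.2.4 repeat this. SAP 6.6.1.1 turns it into a counting rule: the first window starts at the first on-study injection, and "for subsequent injections, it starts from an injection taken after/outside of a previously identified ED". There is no grace period, and a dose at exactly 24 h is not addressed.

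For ITI, Protocol 10.2.7 "will utilize single injections of rFVIII Fc 200 IU/kg, daily", and SAP 3.1.2.3 adds: "Duration of ITI treatment is up to 33 months". For dosing-interval compliance, SAP 6.6.2.2 allows 24 h either side of the prescribed interval, "or +/- 12 hours for ITI regimens, as these are daily dosing or more frequent".

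EDs per patient per year is a secondary endpoint (SAP 2.2.2). SAP 7.4.6 refers its analysis to 6.6.1.1, where EDs are tabulated by treatment regimen, including ITI, and by inhibitor subgroup. EDs also set the denominator of the primary analysis (SAP 9.4.3.2), which is "based on all patients who have reached at least 10 EDs and had at least one inhibitor test performed at or beyond this milestone", together with every patient who develops an inhibitor.

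**The concern.** A reader of an ED table expects a child dosed once a day for a year to show about 365 EDs. Under this rule a dose at 08:00 followed by one at 07:50 next morning is a single ED. The second dose is fully compliant under SAP 6.6.2.2 but leaves no trace in the ED count. The total then depends on minutes of variation in recorded injection times as well as on exposure. At stake are the ITI-regimen and inhibitor-subgroup ED figures. They could look inconsistent with the average daily dose and dosing interval that SAP 6.6.1.3 reports for the same children.

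**Working it through.** The documents give no expected ratio of EDs to doses and no distribution of injection times, so there is no plan figure to reproduce.

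**Inputs from the documents.** The counting rule (SAP 6.6.1.1); one ITI injection daily (Protocol 10.2.7); up to 33 months (SAP 3.1.2.3); ITI intervals compliant within 12 h of plan, that is 12 to 36 h (SAP 6.6.2.2); prophylaxis every 3 to 5 days (SAP 3.1.5.2). **Assumptions.** The timing patterns below; a dose at exactly 24 h opens a new ED.

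**Step 1: bounds.** After a dose opens an ED, the next dose may be absorbed. The one after that comes at least 12 + 12 = 24 h after the opening if both intervals are compliant, so it opens a new ED. At most every second dose is lost, and the share of doses counted lies between 0.50 and 1.00.

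**Step 2: independent scatter around a fixed hour.** After an opening, doses keep opening EDs as long as each is later in the day than the one before. The chance that the first k are in ascending order is 1/k!, so the mean run of counted doses is

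1/1! + 1/2! + 1/3! + … = e − 1 = 1.718.

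Each run ends with one absorbed dose, so the mean cycle is e = 2.718 doses and

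share counted = (e − 1)/e = 1 − 1/e = 0.632.

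The size of the scatter cancels. Simulation of 200,000 daily doses gave 0.631 to 0.633 for scatter from ±15 min to ±11.9 h.

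**Step 3: other assumed patterns for long daily courses.**

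| Pattern | Share counted |
|---|---|
| Same recorded time every day, or steadily later | 1.00 |
| Weekend doses 2 h later (Monday's dose lost: 6/7) | 0.86 |
| 80% of doses at one recorded time, rest within ±1 h | 0.84 |
| SD 0.5 h, times rounded to 60 / 30 / 15 min | 0.77 / 0.69 / 0.66 |
| Independent intervals of 24 ± 1 h | 0.67 |
| Autocorrelated times (0.5 to 0.9) | 0.65 to 0.66 |
| Steadily earlier (5 min a day) | 0.50 |

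The exact-24-h convention matters as well. With identical recorded times every day, the share is 1.00 if a dose at 24 h opens an ED. It is 0.50 if that dose belongs to the old window, because every second dose is then absorbed.

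**Step 4: short daily courses under the Step 2 model.**

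| Daily doses | Mean EDs | Share |
|---|---|---|
| 2 | 1.50 | 0.75 |
| 3 | 2.16 | 0.72 |
| 5 | 3.43 | 0.69 |
| 7 | 4.69 | 0.67 |
| 10 | 6.58 | 0.66 |
| 28 | 17.98 | 0.64 |

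**Step 5: size for ITI under the Step 2 model.** One year: 365 doses give about 231 EDs. A full course: 33 × 30.4375 = 1,004 nominal daily doses, and 1,004 × 0.632 = 635 EDs. This ignores interruptions and the washouts for half-life sampling.

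**Step 6: prophylaxis.** Dosing every 2 to 5 days with ±12 h scatter gives a share of 1.00.

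**Step 7: where ITI EDs can reach.** ITI starts only after a positive inhibitor. SAP 9.4.3.2 puts every inhibitor patient in both numerator and denominator whatever the ED count, and the supporting incidences in SAP 9.4.3.3 use the same method. On the Kaplan-Meier axis the event comes before ITI, and the censored patients are those without an inhibitor. ITI EDs enter none of these. They do enter the ITI-regimen and inhibitor-subgroup totals, and they count towards 50 EDs for a child on ITI.

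**The case against.** The strongest reply is that the SAP only makes the protocol's own definition operational. That is correct: this is not a departure from the protocol, and the same unit drives the milestone visits, the interim analysis and the end of study.

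Three stronger readings are tempting, and the documents do not support them.

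- **That 63% of dosing days is simply what the rule yields.** It is the long-run value under one timing model that the documents do not give. It does not carry over to short bleed or surgery courses, and Protocol 10.2.4.1.2 expects most bleeds to resolve with one dose. Nor is every early dose lost: the test is time since the current ED opened, so the dose after an absorbed one counts even if it is early.
- **That understated ITI exposure distorts the primary endpoint.** Step 7 rules this out under the SAP's analysis. What remains is narrow: an inhibitor-free child who had daily bleed or surgery courses and left near 10 EDs could drop out of the denominator, and such courses before an inhibitor or censoring could shift the ED axis slightly. A 5-dose daily course would shift it by about 5 − 3.4 = 1.6 EDs. The documents give no frequency for either case.
- **That the definition should be replaced throughout.** A calendar rule has the opposite fault, since doses at 23:00 and 01:00 become two EDs. It would also change the unit of the milestones during the study.

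It also stands that ITI exposure is visible elsewhere (injections by reason, average daily dose, dosing interval) and that the ED categories stop at 100 or more. For the 50-ED milestone, daily ITI alone would take about 50/0.632 = 79 days instead of 50, which is short against a course of up to 33 months.

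**Conclusion.** The point holds for ED totals under daily dosing. During ITI the count falls short of dosing days by about 37% on long courses if injection times scatter independently around a fixed hour. The range is 0 to 50% over all compliant once-daily patterns, given that a dose at exactly 24 h opens a new ED. Daily courses of 2 to 7 doses lose about 25 to 33% under the same scatter model. The mechanism follows from the SAP text; the percentages rest on assumed timing. The consequence is a secondary-endpoint figure for ITI and inhibitor patients that can mislead. It is not a threat to the primary inhibitor incidence, and prophylaxis every 3 to 5 days is untouched.

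**What to change.** Keep the 24-hour definition for the ED milestones, the interim and end-of-study triggers, and the primary denominator. Then:

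1. In SAP 6.6.1.1 and 7.4.6, add a calendar-date count (one ED per calendar date with at least one injection) beside the rolling count in the ITI-regimen and inhibitor-subgroup tables.
2. In the SAP 9.4.3.3 summary of EDs at inhibitor onset, give the calendar-date count as a sensitivity figure.
3. In SAP 6.6.1.1, state that a dose at exactly 24 h opens a new ED.
4. Declare the addition in SAP Section 10.

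The cost is one extra derivation and two ED figures for daily-dosed children, with a footnote explaining why they differ. No protocol change is needed.

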6.6.1.2. Duration of rFVIII Fc Dosing

The duration of rFVIII Fc dosing will begin from the first rFVIII Fc dose (episodic or prophylactic) and end with the last rFVIII Fc dose, regardless of the reason for the last dose (e.g.,

prophylaxis, to treat a bleeding episode, surgical). Duration will be calculated as the date of the last dose minus the date of the first dose +1. Any interruptions to dosing will not be accounted for when calculating this duration.

The number and percentage of patients whose duration of dosing was at least 13, 26, 39, 52, 65, 78, 91, 104, 117 and 130 weeks (2.5 years) will be summarized based on the integer part of the calculated week nominal for the Safety Analysis Set.

Duration of rFVIIIIFc dosing (weeks) will also be summarized using descriptive statistics for the Safety Analysis Set. Weeks will be represented in the descriptive statistics as if these were data collected with 1 decimal place.

These tables will be presented by treatment regimen and for the inhibitor subgroups, as described in Sections 5.1.1.1 and 5.1.1.2 respectively.

Duration of rFVIIIIFc dosing will also be summarized by EPD entry compliance (see Section 6.6.2.3), <80% and >=80%, where >=80% is considered compliant.

6.6.1.3. Prophylactic Dose (IU/kg) and Dosing Interval (days)

The prescribed prophylactic dose and dosing frequency will be summarized categorically for the prophylactic and ITI treatment periods.

Because dosing in this study is based on variable doses and dosing intervals, average weekly dose (daily for the ITI treatment regimen) and average dosing interval will be derived for each patient to characterize the amount of rFVIIIIFc received for prophylaxis. Descriptive statistics will be provided using the FAS.

The average weekly (daily for ITI) prophylactic dose (IU/kg) and the average prophylactic dosing interval will be based on prophylactic doses that are not separated by a bleeding episode or major surgical/rehabilitation period. Data to be included in the calculations, specifically the prophylactic doses and the total duration of prophylactic treatment, will come strictly from intervals representing two consecutive prophylactic doses (PR) during the efficacy period (see Section 5.4.2 for a description of the efficacy period). The sum of doses at PR_x and the sum of interval durations (PR_{x+1} minus PR_x) will be determined across all evaluable intervals of PR_x to PR_{x+1}. As such, when an event (a bleeding episode or surgery) is encountered, the interval stops at the prophylactic dose prior to the event and continues with the first prophylactic dose after the event. The last PR dose in the study will be the end of the last interval used for these calculations.

$$\text{Average weekly prophylactic dose} = \frac{\text{Sum of doses at PR}_x \times 7}{\text{Sum of days in PR intervals}}$$

$$\text{Average daily prophylactic dose} = \frac{\text{Sum of doses at PRx}}{\text{Sum of days in PR intervals}}$$

$$\text{Average prophylactic dosing interval} = \frac{\text{Sum of days in PR intervals}}{\text{Number of PR intervals}}$$

Prophylactic dosing will be further characterized by the number of prescribed changes in the dose and the number of prescribed changes in the dosing interval. Dose and dosing interval changes are based on recommendations made by the Investigator and may or may not reflect whatever modifications a patient actually made to his dosing regimen. The number of prescribed changes in the dose level and the number of prescribed changes in the dosing schedule will be summarized categorically (0, 1, 2, 3, 4, >4) and with descriptive statistics.

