- l The rFVIII Fc PK assessments for half-life will be performed at 12-week intervals, only after IR determinations of ≥66% of expected value on 2 consecutive months. The first rFVIII Fc PK assessment will occur 12 weeks after IR≥66% of expected value is confirmed; subsequent PK assessments will be performed every 12 weeks thereafter for subjects who have not yet achieved the criteria for ITI complete success.
- m The subject's parent/caregiver must enter dosing information into the EPD **as soon as possible after an injection and within a maximum of 7 days following the injection** (Section 10.2.4.1.4). It is recommended that parents/caregivers enter dosing information immediately after an injection.
- n Injection site inspection is only to be performed if the subject receives an rFVIII Fc injection during a clinic visit.
- o For subjects who are receiving breast milk, maternal concomitant medications will also be collected at the same time points as other concomitant therapies, unless the breast milk is derived from a source other than the mother or the mother has not consented.

CONFIDENTIAL

The information contained herein may not be used, disclosed, or published without the written consent of Bioverativ Therapeutics Inc.

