#### 4.2.2.4. Schedule of Activities: Pharmacokinetic Sampling for Half-life Determination

Subjects with a confirmed negative inhibitor titer and confirmed IR  $\geq 66\%$  of expected who have not yet achieved the criteria for ITI complete success will undergo PK evaluation for  $t_{1/2}$  every 12 weeks as described in [Figure 2](#); monitoring for inhibitor and IR will continue on a monthly basis. Subjects must not have received an injection of rFVIII Fc within at least 72 hours of the predose sample collection. The PK dose will be 50 IU/kg of rFVIII Fc. Volume and units of factor infused must be calculated and recorded using the *actual* potency as described in the DHA (see Section [10.1.1](#)).

The following Schedule of Activities applies only to subjects requiring PK assessments for determination of  $t_{1/2}$  as described in Section [10.2.7.4.2](#), Section [10.2.7.4.3](#), and Section [10.2.7.6](#).

Activities	Time in Relation to rFVIII Fc Dosing							
	Pre dose a	0	30 min ( $\pm 5$ min)	3 hr ( $\pm 10$ min)	6 hr ( $\pm 10$ min)	24 hrs ( $\pm 60$ min)	48 hrs ( $\pm 60$ min)	72 hrs ( $\pm 2$ hrs)
rFVIII Dosing		X						
PK Assessments b	X		X	X	X	X	X	X

Hr=hours; min=minutes

a Predose sample is to be collected within 30 minutes prior to the start of rFVIII Fc injection.

b Timepoints for PK assessment are measured from start of the rFVIII Fc injection.

CONFIDENTIAL

The information contained herein may not be used, disclosed, or published without the written consent of Bioverativ Therapeutics Inc.

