#### 10.2.7.1. Assessment of Incremental Recovery and Half-Life During Immune Tolerance Induction Therapy

Upon the confirmation of a negative inhibitor titer, IR and  $t_{1/2}$  will be performed per the schedule of assessments (Section 4.2.2.3). Doses given for the purposes of full PK measurements (that is,  $t_{1/2}$ ), and IR will be calculated and recorded using the *actual* potency written on the vial as described in Section 10.1.1. IR and  $t_{1/2}$  assessments will be based on the one-stage clotting assay. The IR and  $t_{1/2}$  will be calculated by the Sponsor and provided to the PI.

For PK assessments, the subject must not be currently bleeding:

- Blood samples for recovery assessments will be taken predose (within 30 minutes prior to the start of the injection) and at 30 ( $\pm 5$ ) minutes after the start of a 50 IU/kg injection of rFVIII Fc. Subjects are required to have at least a 24-hour washout prior to the predose sample collection.
- For PK assessments to determine  $t_{1/2}$ , subjects must not have received an injection of rFVIII Fc within at least 72 hours of the predose sample collection. Sampling will occur at the following time points: predose and 30 ( $\pm 5$ ) minutes; 3 and 6 hours ( $\pm 10$  minutes); and 24 hours ( $\pm 60$  minutes), 48 hours ( $\pm 60$  minutes), and 72 hours

CONFIDENTIAL

The information contained herein may not be used, disclosed, or published without the written consent of Bioerativ Therapeutics Inc.

(±2 hours) after a 50 IU/kg injection of rFVIII Fc. Subjects should not have any additional doses of rFVIII Fc during the PK sampling period. If additional doses are required for clinical care, please immediately inform the Sponsor, as the  $t_{1/2}$  assessments must be repeated.

Whole blood will be drawn for exploratory assays related to immune response during ITI, starting with a sample collected at the pre-ITI assessment visit. A whole blood sample will be drawn every other month during ITI, at the time of the confirmation of complete success, partial success, or failure, and at the end of tapering (if applicable). Up to 10 mL of whole blood (minimum 3 mL) should be collected, as allowable by patient weight and institutional practice regarding blood draw restrictions for pediatric patients.

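### SAP 6.6.1.3 and 6.6.2.2 do not cut ITI dose intervals at protocol-required half-life tests, so a fully adherent child shows less than 200 IU/kg/day and off-schedule intervals

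*SAP*

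**What the plan says.** **Regimen.** Under Protocol 10.2.7, ITI "will utilize single injections of rFVIII Fc 200 IU/kg, daily".

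**Tests during ITI (Protocol 10.2.7.1, 4.2.2.3, 4.2.2.4).**
- For half-life, "subjects must not have received an injection of rFVIII Fc within at least 72 hours of the predose sample collection". Sampling then runs to 72 hours, and "Subjects should not have any additional doses of rFVIII Fc during the PK sampling period". On dose: "The PK dose will be 50 IU/kg of rFVIII Fc".
- On frequency, once IR of at least 66% of expected is confirmed: "The rFVIII Fc PK assessments for half-life will be performed at 12-week intervals". The first test comes 12 weeks after that confirmation. Repeats apply only to children who have not yet met complete success.
- For IR, also with a 50 IU/kg dose: "Subjects are required to have at least a 24-hour washout prior to the predose sample collection". The post-dose sample is at 30 minutes. IR is monitored monthly after a confirmed negative titer.

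**Analysis (SAP).**
- 6.6.1.3 sums doses and days over intervals between consecutive regimen doses in the efficacy period. Its stopping rule is that "when an event (a bleeding episode or surgery) is encountered, the interval stops at the prophylactic dose prior to the event".
- 6.6.2.2 uses the same intervals for interval compliance. The tolerance is 24 hours, "or +/- 12 hours for ITI regimens, as these are daily dosing or more frequent".
- 6.6 lists PK assessment as its own reason for injection, separate from ITI.
- 5.4.2.1 and 5.4.2.2 adjust the efficacy period for surgery and, in prophylactic regimens, for gaps above 28 days. 5.4.5 states that no PK period is defined.
- 6.6.1.4, on consumption, describes the efficacy period as excluding PK assessments.

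**The concern.** A half-life test replaces daily ITI dosing with 72 hours of washout, one PK dose and 72 hours of sampling. A child who follows the protocol exactly therefore has two consecutive ITI doses 6 days apart. Nothing in the SAP's interval rules removes that gap. It lowers his average daily dose, lengthens his average interval and counts as an off-schedule interval.

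The number of such gaps depends on how far the child has responded. A child whose inhibitor never clears has no half-life tests. A child with confirmed IR who has not yet met complete success has one every 12 weeks. Differences in the ITI dose and compliance summaries, between patients or between the interim and final analyses, would then partly reflect the test schedule. Describing experience with ITI is a secondary objective, and SAP section 12 plans tables of ITI dose, ITI interval and ITI compliance.

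**Working it through.** **Inputs.** ITI 200 IU/kg every 24 hours (Protocol 10.2.7). Half-life test: last ITI dose 72 hours before, PK dose at 0, next ITI dose 72 hours after, at nominal sampling times (Protocol 10.2.7.1). Half-life test every 84 days and IR every 28 days (Protocol 4.2.2.3, 4.2.2.4). PK doses are not ITI doses (SAP 6.6). Full adherence is assumed throughout.

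**Formulas (SAP 6.6.1.3, 6.6.2.2).**
- Average daily dose = sum of doses / sum of days in intervals.
- Average interval = sum of days / number of intervals.
- Interval compliance = intervals within 12 hours of 24 hours / number of intervals.

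**Benchmark, no tests.** 84 doses over 84 days: 84 × 200 / 84 = 200 IU/kg/day, 1.000 day, 100%. This reproduces the planned regimen.

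**One half-life test.** The ITI-to-ITI gap is 72 + 72 = 144 hours, or 6 days, which is 120 hours over the prescribed interval. Five daily doses are lost, leaving 84 - 5 = 79.
- Dose: 79 × 200 / 84 = 188.1 IU/kg/day (-6.0%).
- Interval: 84 / 79 = 1.063 days.
- Compliance: 78 / 79 = 98.7%.

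**IR tests.** The documents do not say when ITI resumes after an IR test, so both cases are shown.
- ITI dose given after the 30-minute sample: the interval is about 24.5 hours, within tolerance, and the effect is nil.
- ITI resumed the next day: each IR test costs one dose and creates a 48-hour interval that fails the rule.

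| Per 84 days | ITI doses | IU/kg/day | Mean interval (days) | Compliant intervals |
|---|---|---|---|---|
| No tests | 84 | 200.0 | 1.000 | 100% |
| 3 IR, same-day ITI dose | 84 | 200.0 | 1.000 | 100% |
| 3 IR, next-day ITI dose | 81 | 192.9 (-3.6%) | 1.037 | 78/81 = 96.3% |
| 1 half-life, IR same-day | 79 | 188.1 (-6.0%) | 1.063 | 98.7% |
| 1 half-life + 2 IR, next-day | 77 | 183.3 (-8.3%) | 1.091 | 74/77 = 96.1% |
| 1 half-life + 3 IR, next-day | 76 | 181.0 (-9.5%) | 1.105 | 72/76 = 94.7% |

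A deliberately extreme schedule (IR every 14 days with next-day resumption, plus half-life every 84 days) gives 173.8 IU/kg/day and 90.4%, still above the 80% cut-off.

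**Cumulative example.** Assume negative titer at week 12, IR confirmed at week 20, same-day ITI dosing after IR, and ITI to 33 months (1,004 days).
- Day 140, no half-life test: 200.0.
- Day 231, one test: 226 × 200 / 231 = 195.7.
- Day 315, two tests: 305 × 200 / 315 = 193.7.
- Day 1,004, ten tests: 954 × 200 / 1,004 = 190.0.

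No planned dose was missed at any point.

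**If the PK dose were counted as a regimen dose.** (79 × 200 + 50) / 84 = 188.7 IU/kg/day, and two 72-hour intervals fail instead of one. The effect remains.

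**With the windows cut.** Dropping each interval that contains a test window returns 200.0 IU/kg/day, 1.000 day and 100% in every 84-day scenario tabulated above.

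**The case against.** **SAP 6.6.1.4 already excludes PK assessments from the efficacy period, and 6.6.1.3 is confined to that period.** This is the best counter-text, and it indicates what was intended. But it sits in the consumption section, 5.4.2 contains no such adjustment, and 5.4.5 defines no PK period from which days could be removed. Sections 6.6.1.3 and 6.6.2.2 name only bleeds and surgery. The defect is thus an exclusion stated in one place and carried out nowhere, and two programmers could reasonably differ.

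**SAP 6.6.2.2 lets Investigator instructions on interval changes define the prescribed interval.** If every hold were recorded that way, the compliance effect would disappear. Average dose and interval would still be uncut, and the holds would add to the counts of prescribed schedule changes in 6.6.1.3.

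**The child really does receive less drug during a test, and 6.6.1.3 aims to characterize the amount received.** This is fair, and it is why the days removed should be reported. However, the SAP already sets aside stretches around bleeds and surgery, so its average describes the regimen outside interruptions. For compliance the argument does not help, because a hold required by the protocol is scored as off-schedule.

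**Little depends on it.** This stands. These are descriptive summaries in the ITI subset, and the planned listings show injection reasons and test results.

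**Two stronger readings are tempting.** A reader might infer that the planned tables will show ITI intensity falling with time on ITI. They will not: 6.6.1.3 gives one average per patient, and section 12 lists no ITI dose or interval table by time on ITI. A reader might also infer that a child looks worse the closer he is to success. A child who passes his first half-life test has at most one window (about -2% at day 231 in the example above). Repeated windows accrue to children who have confirmed IR but have not met complete success. Nor is early ITI necessarily free of tests: the Protocol 4.2.2.3 schedule marks IR from ITI Week 4, while 13.3 makes it discretionary during inhibitor positivity.

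**Conclusion.** The point holds as a minor inconsistency in the SAP. As written, the interval rules leave a gap of at least 6 days for every half-life test, and a fully adherent child is shown below the planned dose and with non-compliant intervals. In the half-life phase the understatement of average daily dose is 6% from half-life tests alone, and 8.3% if ITI resumes the day after the other two IR tests. IR testing by itself contributes between 0 and -3.6%, depending on a resumption time the documents do not give.

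The figures assume full adherence, nominal test timing, PK doses kept separate from ITI doses, and holds not recorded as prescribed interval changes. The distortion grows with the number of half-life tests after IR is confirmed, so it matters for comparisons between patients and between the interim and final analyses. On the planned schedule, test windows alone do not move a child below the 80% compliance class. ITI response and the primary endpoint do not use these quantities.

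**What to change.** In SAP 6.6.1.3 and 6.6.2.2, add a PK assessment window to the events that stop and restart the interval series, alongside bleeds and surgery. Define the window as running from the last regimen dose before the washout to the first regimen dose after the last sample. Align the wording with the exclusion stated in 6.6.1.4, so that all three sections follow one rule. Report the number of windows and the total days removed, per patient and overall, so that the amount actually received stays visible.

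The cost is a sentence or two in the SAP and a small programming change. PK injections already carry their own reason code, so the intervals can be identified from data already collected. No clinical procedure changes.
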